10.0 STUDY ASSESSMENTS

10.1 Visit 1 (Day 1 - Screening Visit, enrolment and start of treatment)

Before any screening procedure the patients have to sign and date the current version of the Informed Consent Form.

During Visit 1 the following information will be recorded:

- Demography
- Medical and surgical history, and underlying diseases
- Previous medications (not ongoing) in the last 2 weeks
- Concomitant medications (ongoing at the time of the visit, including any compound prescribed for the routine treatment of the target lesion)
- Vital signs
- Clinical evaluation
- Wound examination
- Check of Inclusion/exclusion criteria
- AEs monitoring (AEs will be monitored from the Informed Consent signature to Day 15)
- Treatment prescription/First treatment administration
- Diary distribution

10.2 Visit 2 (Day 8, Control Visit)

During Visit 1, the following information will be recorded:

- Concomitant medications (started before the patient's enrolment in the study and ongoing during the study, or started during the patient's participation in the study and including any compound prescribed for the routine treatment of the target lesion)
- Wound examination
- 5- point VRS evaluation (recorded by the patient on the Diary; Day 1-8)
- 11-point Numerical Pain Rating Scale evaluation (recorded by the patient on the Diary; Day 1-8)
- AEs/SAEs monitoring
- Patient's Diary revised by the Investigator

10.3 Visit 3 (Days 15, End of Study)

During Visit 2 the following information will be recorded:

- Concomitant medications (started before the patient's enrolment in the study and ongoing during the study, or started during the patient's participation in the study and including any compound prescribed for the routine treatment of the target lesion)
- Vital signs
- Wound examination
- 5- point VRS evaluation (recorded by the patient on the Diary; Day 9-15)
- 11-point Numerical Pain Rating Scale evaluation (recorded by the patient on the Diary; Day 9-15)
- AEs/ SAEs monitoring
- Patient's Diary revised by the Investigator for completeness and accuracy and collected

10.4 Details of Individual Assessments

10.4.1 Demography, Medical, Surgical history and Clinical Evaluation

A full demography, medical and surgical history, underlying diseases and clinical evaluation will be collected at the Visit 1.

10.4.2 Vital Signs

Vital signs (heart rate and blood pressure) will be carried out at the Visit 1 and 3.

10.4.3 Wound examination

A wound examination will be carried out at the Visit 1, 2, 3.

10.4.4 5-point Visual Rating Scale (VRS) evaluations

Five-point VRS will be used by the patient to assess the pain relief over the treatment period. The patients mark on the scale their level of pain relief during the past 24 hours. This information is recorded by the investigator at the Visit 1, 2, 3 in the hospital record and by the patient daily in the diary.

10.4.5 11- point Numerical Pain Rating Scale evaluation

Eleven-point NPPS will be used by the patient to assess the pain intensity over the treatment period. This information is recorded by the investigator at the Visit 1, 2, 3 in the hospital record and by the patient daily in the diary.

10.4.6 Safety Evaluations

All AEs will be recorded from informed consent signature up to the end of the study

11.0 REPORTING SAFETY INFORMATION

11.1 Definitions

Adverse Event (AE): as any untoward medical occurrence in a patient or clinical trial subject administered a medicinal product and which does not necessarily have a causal relationship with this treatment.

An AE can therefore be any unfavourable and unintended sign (including an abnormal laboratory finding), symptom, or disease temporally associated with the use of a medicinal (investigational) product, whether or not related to the medicinal (investigational) product.

In clinical studies, an AE can include an untoward medical occurrence occurring at any time, including run-in or washout periods, even if no study treatment was administered.

Non-serious AE: any untoward change in a patient's medical health that does not meet serious criteria noted below (e.g., is not life-threatening, does not require hospitalization, does not prolong a current hospitalization, is not disabling, etc.).

Serious adverse event (SAE): any adverse experience that meets any of the following criteria:

- Results in death.
- Is life-threatening.

The patient was at immediate risk of death at the time of the event; it is not referred to cases in which the event might have caused death if it was more severe.

- Requires inpatient hospitalization or prolongation of existing hospitalization.

In general, hospitalization signifies that the individual remained at the hospital or emergency ward for observation and/or treatment (usually involving an overnight stay) that would not have been appropriate in the physician's office or an out-patient setting.

- Results in persistent or significant disability/incapacity.

The term disability means a substantial disruption of a person's ability to conduct normal life functions. This definition is not intended to include experiences of relatively minor medical significance such as uncomplicated headache, nausea, vomiting, diarrhoea, influenza, or accidental trauma (e.g., sprained ankle) which may interfere or prevent everyday life functions but do not constitute a substantial disruption.

- Is a congenital anomaly/birth defect.
- Is an important medical event.

An important medical event is an event that may not result in death, be life-threatening, or require hospitalization but may be considered an SAE when, based upon appropriate medical judgment, it may

jeopardize the patient and may require medical or surgical intervention to prevent one of the outcomes listed in the definitions for SAEs.

Suspected Unexpected Serious Adverse Event (SUSAR): a serious adverse reaction (AR) which is not consistent with the information about the concerned drug. The reference information is included in the Summary of product characteristics (SmPC).

11.2 Monitoring for Adverse Events

At each visit, after the patient has the opportunity to mention spontaneously any problems, the Investigator or appropriate designee should inquire about AEs by asking the standard questions:

- “Have you had any health problems since your last study visit?”
- “Have there been any changes in the medicines you take since your last study visit?”

AEs should be reported for any clinically relevant change in concomitant medication(s) that is the result of an untoward (unfavourable and unintended) change in a patient's medical health. These clinically relevant changes is reported regardless of causality.

11.3 AEs Recording by the Investigator

All **Adverse Events** (non-serious and serious) which occur during the course of the study will be recorded in the CRF. Any pre-existing medical conditions or signs/symptoms present in a patient prior to the start of the study (i.e., before informed consent is signed) should be entered in medical history section in the CRF. After the informed consent has been signed, all untoward medical occurrences that occur during the course of the study must be documented in the Adverse Event section of the CRF. Whenever possible, signs and symptoms indicating a common underlying pathology should be documented as one comprehensive event.

For each recorded event, the AE documentation must include the onset date, outcome, resolution date (if event is resolved), intensity (for the intensity/severity assessment see below), any action with study treatment taken as a result of the event, and an assessment of the adverse event's relationship to the study treatment (for the causality assessment see below).

11.3.1 AE - Intensity and Causality Assessment

For **every AE**, the Investigator must assess the intensity (severity) and causality (relationship to study treatment) according to the following criteria:

Intensity /Severity

Mild	Grade 1 - Does not interfere with patient's usual function (awareness of symptoms or signs, but easily tolerated [acceptable]).
Moderate	Grade 2 - Interferes to some extent with patient's usual function (enough discomfort to interfere with usual activity [disturbing]).
Severe	Grade 3 - Interferes significantly with patient's usual function (incapacity to work or to do usual activities [unacceptable])

Causality:

ADVERSE REACTION	UNRELATED/ UNLIKELY RELATED	Temporal relationship to study treatment administration is not plausible	OR	There are no reasonable grounds for suspecting that the product could have caused the event AND other causes (e.g., treatments or underlying diseases) provide plausible explanations
	POSSIBLY RELATED	Temporal relationship to study treatment administration is plausible	BUT	The event can reasonably be explained by other equally or more likely causes
	PROBABLY/ CERTAINLY RELATED	Temporal relationship to study treatment administration is plausible	AND	The event is more likely explained by the treatment than by other causes or there are no other causes that can explain the event

11.4 SAEs Recording and Reporting by the Investigator to SOFAR

The Investigator must record all **Serious Adverse Events** occurred during the study, regardless of presumed causal relationship, in the Serious Adverse Event form and forward it to SOFAR pharmacovigilance by [contact] or e-mail: [contact].

The assessment of seriousness is performed by the Investigator on the basis of criteria provided in the section 11.1.

The Investigator must provide SOFAR with the SAE form within 24 hours from the knowledge of the event. The initial SAE form must include at least the minimal four information to identify the event: patient enrolment number, investigational drug, nature of the adverse event and reporter/Investigator identification.

Depending on the nature and seriousness of the adverse event, SOFAR may request copies of appropriate medical records of the patient (identified by the enrolment number and not by personal identification data) as well as results of laboratory tests performed. If the patient was hospitalized a copy of the discharge summary must be provided to SOFAR as soon as available.

Follow-up SAE information should be provided to SOFAR whenever the investigator becomes aware of new available information regarding the SAE, once the condition is resolved or stabilized and when no more information about the event is expected.

11.5 SAE - Causality and Expectedness Assessment by SOFAR

The sponsor should not downgrade the causality assessment given by the investigator.

An assessment of **expectedness and causality of each SAE** will be performed case by case, when appropriate, by SOFAR within 7 calendar days from the receipt of a serious adverse event, within 1calendar day from the receipt in case of death or life threatening events.

11.6 Follow-Up of Patients with Serious Adverse Events

The Investigator is responsible for adequate and safe medical care of patients during the study and for ensuring that appropriate medical care and relevant follow-up procedures are maintained after the trial. A follow-up SAE report will be filled in by the investigator if important follow-up information (i.e. diagnosis, outcome, causality assessment, results of specific investigations) are made available after submission of the initial SAE form. Follow-up SAE forms will be sent to SOFAR as described above for the initial submission.

In any case of an AE that, in the opinion of the Investigator, requires the subject's discontinuation, follow-up information relating to the patients subsequent course must be collected until the event has subsided or the condition stabilised.

11.7 Reporting Procedure to ECs and Competent Authorities

The notification to the ECs and Competent Authorities will be performed by SOFAR according to the post-marketing surveillance regulations.

12.0 STATISTICAL METHODS

12.1 Sample Size Calculation

The sample size calculation takes into account the type of study design, before and after study with two main pain assessments (at baseline and at the end of treatment). Limited to the hypotheses tests that will be run on pain relief and pain intensity, the sample was sized by assuming a standardized effect size equal to 0.35, for a one-tailed test with a 5% significance level and a power equal to 90% (Woodward, 2005). As a consequence 70 evaluable patients are needed for the study. Supposed that a 10% of screening failure is expected the total number of patients to be enrolled is 78.

12.2 Hypothesis Testing

For the first primary endpoint (pain relief) a one-sided test will be carried out, so that the two hypotheses under consideration are:

$$H_0: \mu = \mu_0 = 0 \quad \text{vs.} \quad H_A: \mu > \mu_0$$

where μ is the population parameter representing mean pain relief at the end of treatment.

A similar null and alternative hypothesis will be tested for the second primary endpoint (pain intensity):

$$H_0: \delta = 0 \quad \text{vs.} \quad H_A: \delta > 0$$

where δ is the population parameter representing mean difference in pain intensity before and after treatment. In order to control the Type I error that results from the multiplicity of endpoints, test of significance for the second primary endpoint will only be made if the primary analysis results in significant treatment effects at $p < 0.05$. In that event, a suitable strategy to deal with multiple endpoints will be adopted (16, 17).

12.3 Study Populations

The primary analyses for efficacy outcome variables will be performed on the Full Analysis Set (FAS) population, defined as all patients enrolled in this study. Descriptive statistics will be provided for demographical or clinically relevant characteristics.

Per-protocol (PP) population will be defined as the subset of the Full Analysis Set population defined by the exclusions of subject with at least one major protocol deviations (e.g. low compliance to treatment, use of prohibited concomitant medications). A per-protocol analysis has been planned only for the primary endpoint.

All patients who applied at least one dose of ORTODERMINA® will be included in the safety population.

12.4 Statistical Analyses

The statistical analyses will be performed by Eudax. No interim analysis has been planned.

Baseline and end of treatment characteristics (Vital signs, and Clinical evaluation, Wound examination) of the patients will be evaluated by descriptive analysis (e.g., median, mean, standard deviation, minimum, maximum for continuous data; frequency tables for categorical data).

12.5 Efficacy Data

The primary analysis of efficacy will be based on the FAS population.

Efficacy will be evaluated according to an improvement in the pain relief (5-point Visual Rating Scale -VRS) and to the reduction of pain intensity (11-point Numerical Pain Rating Scale).

Wound pain relief from baseline (V1, Day 1) to end of treatment (V3, Day 15) will be analysed with a one-sample t-test, assuming a reference value equal to 0 (no relief) at baseline. Improvement in the pain relief will be observed with VRS scores at end of treatment significantly greater than 0.

Differences in pain Intensity from baseline (V1, Day 1) to end of treatment (V3, Day 15) will be analysed with a two-paired samples t-test. Improvement in the pain intensity will be observed with NPRS scores at end of treatment significantly lower than those at baseline.

All assessments coming from patient's pain daily diary concerning both relief and intensity will be reported descriptively and graphically.

Patients who will withdraw their consent before treatment start and who will fail to meet the inclusion criteria will be excluded from efficacy analysis.

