Exclusion Criteria:	
 Patients with ulcer infected, discoloured, odorous, pressure ulcer grade I, III, or IV (according to NPUAP classification – Appendix 3) Diabetic foot ulcer Patients with contraindication or known allergy to drug's components Patients with known severe allergies manifested by a history of anaphylaxis, or history or presence of severe multiple allergies Female patients who are pregnant or lactating. Patients with vascular disorders (mainly arteriopathies) Patients known as alcohol or drug abusers. Patients currently participating in a clinical study
Treatment	Local treatment with ORTODERMINA® over 14 days period (once a day)
Prohibited medication	Other compounds containing Lidocaine
Planned Sample Size and Statistical Methods	
A sample size of 70 evaluable patients is needed to test the hypotheses of an improvement in wound pain relief and of a reduction in pain intensity, assuming a standardized effect size equal to 0.35, for a one-tailed test with a 5% significance level and a 90% power. Supposed that a 10% of attrition rate is expected the total number of patients to be enrolled is 78.
 
Differences in wound pain relief from baseline to end of treatment will be analysed with a one-sample t-test, assuming a reference value equal to 0 at baseline; changes in pain intensity with a two-paired samples t-test.

Planned Study Timelines:	
FPFV: First quarter 2015
 
LPLV: First quarter 2016

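### The first primary test compares mean Day 15 pain relief with 0, the floor of its scale, so its p-value says almost nothing as a success criterion or as the gate to the pain-intensity test

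*Combined protocol and SAP*

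**What the plan says.** Section 12.2 sets a one-sided test of mean = 0 against mean > 0 for the first primary endpoint, where the mean "is the population parameter representing mean pain relief at the end of treatment". Section 12.5 says that relief from V1 to V3 (Day 15) "will be analysed with a one-sample t-test, assuming a reference value equal to 0 (no relief) at baseline", and gives the success rule "Improvement in the pain relief will be observed with VRS scores at end of treatment significantly greater than 0". The synopsis repeats it: "analysed with a one-sample t-test, assuming a reference value equal to 0 at baseline".

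Appendix 1 prints the relief scale with anchors from 0 (no relief) to 4 (complete relief). It has no value for worsening. The same appendix describes a 100 mm line scored in millimetres from the left-hand end.

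The second primary endpoint is the change in pain intensity on the 0-10 NPRS, tested with a paired t-test. Under section 12.2, "test of significance for the second primary endpoint will only be made if the primary analysis results in significant treatment effects" at p<0.05, after which "a suitable strategy to deal with multiple endpoints will be adopted". The synopsis states that 70 evaluable patients are "needed to test the hypotheses of an improvement in wound pain relief and of a reduction in pain intensity", at a standardized effect of 0.35, one-tailed 5% and 90% power. Section 12.5 adds that all assessments from the "pain daily diary concerning both relief and intensity will be reported descriptively and graphically".

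**The concern.** A test against 0 is sound when scores can fall on either side of 0, because deterioration then pulls the mean down. Here 0 is the lowest score available. It is an assumed reference at the bottom of the scale, not a measured comparator. Two things follow.

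- The null is true only if every patient scores exactly 0. The standard deviation is then 0 and t is undefined, so the 5% level has no practical meaning.
- Any positive scores move the mean off the null, and nothing can move it back.

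At stake is what a significant first primary endpoint would mean. Section 12.5 would call it improvement and section 12.2 a significant treatment effect, although 65 of 70 patients might have reported no relief. The same result opens the gate to the NPRS test, so the gate would filter out almost nothing.

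**Working it through.** **Inputs.** n = 70 evaluable, one-sided 5%, effect 0.35, power 90% (12.1); test against 0 (12.2, 12.5); scale 0-4 or millimetres (Appendix 1). The documents do not say what share of patients would report relief, so 2% to 20% is assumed below.

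**1. The plan's own figure.** n = ((1.645 + 1.282)/0.35)² = 69.91, rounded up to 70; 70/0.9 = 77.8, rounded up to 78. Both reproduce. By the noncentral t distribution, power at n = 70 is 89.5%.

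**2. How few non-zero scores suffice (whole numbers 0-4).** t = mean/(SD/√n), critical value 1.667 on 69 df. For k scores of 1 and the rest 0, t = √(k(n−1)/(n−k)).

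- Five scores of 1: √(5×69/65) = 2.304, p = 0.012.
- Least favourable five (1,1,1,1,4): mean 8/70 = 0.114; sum of squares about the mean 20 − 64/70 = 19.09; SD 0.526; t = 0.114/(0.526/8.367) = 1.818, p = 0.037.

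All combinations of k non-zero scores from 1 to 4, the rest 0:

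| k | combinations | with p<0.05 | range of p |
|---|---|---|---|
| 2 | 10 | 0 | 0.079-0.114 |
| 3 | 20 | 11 | 0.042-0.079 |
| 4 | 35 | 34 | 0.022-0.054 |
| 5 | 56 | 56 | 0.012-0.037 |

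The one failing set of four is 1,1,1,4 (p = 0.054). The counts are the same at n = 78.

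**3. How often the test is met.** If all non-zero scores are 1, three suffice. With 10% reporting relief, P(at least 3 of 70) = 1 − (0.0006 + 0.0049 + 0.0187) = 0.976. The 0-4 columns below give the range over six mixes of scores (all 1; even over 1-4; 50/30/15/5% on 1/2/3/4; and 50/50, 80/20 and 90/10 on 1/4), by simulation with 200,000 runs. The millimetre column assumes that patients with relief mark evenly over 1-100 mm.

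| share with any relief (assumed) | test met, 0-4 | test met, mm | two-sided 95% CI excludes 0, 0-4 |
|---|---|---|---|
| 2% | 7-17% | not run | not run |
| 5% | 47-69% | 49% | 23-47% |
| 10% | 92-98% | 92% | 79-93% |
| 20% | at least 99.9% | over 99.9% | at least 99.8% |

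**4. Isolating the floor.** Suppose 10% of patients improve by one point, 10% worsen by one point and 80% do not change, so the true mean change is 0. The paired test rejects in about 5% of trials. The same data with worsening recorded as 0 reject in about 98%. This example treats one point of change as one point of relief, for illustration only.

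**5. Millimetre scoring.** With marks of 100,1,1,1,1 and 65 zeros: mean 104/70 = 1.486; sum of squares about the mean 10,004 − 10,816/70 = 9,849.5; SD 11.95; t = 1.486/(11.95/8.367) = 1.04, p = 0.151. Five non-zero marks are therefore not always enough, but the floor is the same.

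**The case against.** The strongest defence has four parts.

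- **The test is uninformative rather than invalid.** If every score were 0 it could not reject, so it does not exceed its nominal level. That stands, but a success rule that a few non-zero scores satisfy still cannot do its job.
- **The NPRS test protects the study.** It can register worsening and can fail. A reader might infer that the weak gate inflates its error rate. It does not: a gate that is almost always open leaves the NPRS test at its own 5% level. The relief claim, however, would stand alone under the rule in 12.5.
- **The data will be visible anyway.** Section 12.5 already plans descriptive and graphical reporting of the diary. That helps the reader but does not remove the success rule.
- **The five-score result depends on the scoring.** This is correct. A reader might take it as true of any scoring, and the millimetre rule in Appendix 1 does not support that.

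A reader might also argue that relief could come from the other therapies that section 7.1 allows. That is a limit of the single-arm design. It affects NPRS change equally and is no part of this point.

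**Conclusion.** The point holds as wrong as written. The first primary success criterion cannot register worsening and is met almost automatically once about one patient in ten reports any relief: 92-98% of trials under 0-4 scoring, and 92% under millimetre scoring with evenly spread marks. The five-score result needs whole-number scoring and the planned one-sided test. The shares reporting relief are assumptions, and at 5% the test is met in only about half to two-thirds of trials.

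A reader might infer that a confidence interval excluding 0 is just as easy to obtain. At a 5% share it is not (23-47% against 47-69%). The case for caution with the interval is simply that the scale cannot go below 0. The stated sample size is not in question here.

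**What to change.** 1. **12.1, 12.2, 12.5 and synopsis:** make the paired NPRS change from V1 to V3 the formal test at one-sided 5%. In 12.2 delete the relief hypotheses, the gate and the sentence on a multiple-endpoint strategy; with one test they have no purpose.
2. **12.5 and synopsis:** replace the test of relief against 0 and its success rule with the Day 15 VRS distribution and mean relief with a 95% CI, on one named Appendix 1 scoring. State that a CI excluding 0 is not by itself evidence of efficacy, because the scale cannot go below 0.
3. **12.5:** amend the sentence that makes improvement in relief an efficacy criterion, so that efficacy is judged on NPRS and relief is described.
4. **12.3:** state that the per-protocol analysis covers the NPRS test and the VRS estimate.

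Relief can remain a primary end-point in 6.1, since the objective in 5.1 is to observe it.

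**Cost.** An amendment with Ethics Committee approval before use (15.1); no extra patients or assessments. Power for the NPRS test is 89.5% at 0.35 SD with n = 70. The downside is that relief loses its formal test. Its CI would have a half-width of 1.995 × SD/√70, about 0.12 to 0.36 points on 0-4 scoring for an assumed SD of 0.5 to 1.5. If the sponsor wants to keep a test of relief, it must pre-specify and justify a non-zero minimum relief or a responder threshold, which the documents do not give, and place that test after the NPRS test.

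### The Day 15 t-tests cannot use enrolled patients who lack a Day 15 rating and no rule covers them, so pain-related loss may bias both primary results in either direction

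*Combined protocol and SAP*

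**What the plan says.** **Population.** Section 12.3 places the primary efficacy analysis on the FAS, "defined as all patients enrolled in this study". Section 12.5 takes out only patients who withdraw consent before treatment or fail the inclusion criteria.

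**Tests (12.5).** Pain relief is a one-sample t-test of the Day 15 VRS score against an assumed baseline of 0, so it uses no Day 1 rating. Pain intensity, from Day 1 to Day 15, "will be analysed with a two-paired samples t-test". Under 12.2 the VRS is tested first, and the NPRS only if the VRS result is significant.

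**Daily ratings.** Sections 3.0 and 14.2 have the patient rate both scales every day from Day 1 to Day 15. For Visit 3, for example, section 10.3 lists "11-point Numerical Pain Rating Scale evaluation (recorded by the patient on the Diary; Day 9-15"). The planned use of these data is this: "All assessments coming from patient's pain daily diary concerning both relief and intensity will be reported descriptively and graphically". Section 10.4 adds that the investigator also records both scales in the hospital record at Visits 1, 2 and 3.

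**Loss of patients.** The synopsis states: "Supposed that a 10% of attrition rate is expected the total number of patients to be enrolled is 78". Section 12.1 reaches the same 78 but calls the 10% screening failure. Section 8.5 replaces drop-outs until 70 are evaluable. Section 9.3 restricts the efficacy analysis to patients with at least 80% of applications, and section 9.4 removes users of other lidocaine products from it.

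The plan gives no method for a missing Day 15 rating and no sensitivity analysis for it. The only other planned efficacy analysis is per-protocol.

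**The concern.** A patient without a Day 15 rating stays in the FAS by definition but cannot enter either t-test unless a value is supplied. As written, an analysis labelled all enrolled patients is in practice an analysis of those who reached Day 15. This follows from the plan's silence; it is not a stated exclusion rule.

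The study has one arm, so there is no comparator in which similar losses might offset the effect. Selective loss goes straight into the mean that is tested against zero. Under section 8.4 patients leave at their own request or at the investigator's discretion, so leaving may well be related to pain. The diary ratings given before leaving show how such a patient was doing, yet they take no part in the inference.

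**Working it through.** **1. The plan's own figure.** Inputs from 12.1: standardized effect 0.35, one-sided 5%, power 90%, and a "before and after study with two main pain assessments (at baseline and at the end of treatment").

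- n = ((1.645 + 1.282)/0.35)² = 69.9, so 70. The stated figure reproduces.
- Enrolled: 70/0.9 = 77.8, so 78. This also reproduces.
- Exact (noncentral t) power at 70 is 89.5%.

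The 70 is therefore a count of patients who have both assessments. If 10% of 78 lack Day 15, the tests run on 70, which is the number that 8.5 restores by replacement.

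**2. Bias, by arithmetic.** Let m be the fraction missing, 0.35 SD the effect in completers and d the effect in those missing. The effect in all patients is (1 − m) × 0.35 + m × d. The relative error of the completer mean is 0.35 divided by that, minus 1. The values of d, and the 20% rate, are assumptions; the documents give none.

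| d in drop-outs | m = 10% | m = 20% |
|---|---|---|
| 0 | 0.35/0.315: +11% | 0.35/0.280: +25% |
| 0.175 (half) | 0.35/0.3325: +5% | 0.35/0.315: +11% |
| 0.35 (same) | 0% | 0% |
| 0.70 (double) | 0.35/0.385: −9% | 0.35/0.420: −17% |

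**3. Bias, by simulation.** Assumptions: 78 patients, true effect 0.35, 10% missing, correlation 0.7 between an earlier rating and Day 15, and logistic drop-out with slope 1 per SD. The model-type estimate is a regression on the earlier rating, standing in for a repeated-measures model.

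| Drop-out depends on | Who leaves | Completer mean | Model-type estimate |
|---|---|---|---|
| Earlier rating | Doing poorly | 0.41 | 0.35 |
| Earlier rating | Doing well | 0.29 | 0.35 |
| Unseen Day 15 value | Doing poorly | 0.44 | 0.40 |
| Unseen Day 15 value | Doing well | 0.26 | 0.31 |

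When drop-out follows ratings already recorded, the model removes the bias. When it follows the unseen value, about half remains (0.44 − 0.35 = 0.09 falls to 0.40 − 0.35 = 0.05).

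**4. False-positive rate for the NPRS change.** With no true change, 10% missing, patients doing poorly leaving, correlation 0.5 to 0.7 and slope 1.0 to 1.5 per SD, the completer t-test rejects in roughly 11% to 18% of trials, against a nominal 5%. This does not carry over to the VRS, which cannot fall below 0.

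**5. Precision.** Let ρ be the assumed correlation between the last diary rating and Day 15. The variance of the Day 15 mean is about s²[(1 − ρ²)/70 + ρ²/78], against s²/70 for completers. At ρ = 0.7, the ratio is 70 × (0.51/70 + 0.49/78) = 0.950, and its square root is 0.975. The standard error falls by 0.5%, 1.3%, 2.6% and 4.2% at ρ = 0.3, 0.5, 0.7 and 0.9. The ceiling is 1 − √(70/78) = 5.3%. Power moves from 89.5% to between 89.5% and 91.6%.

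**6. Cost of a no-improvement analysis.** With 70 completers at 0.35 SD and 8 patients set to 0:

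- mean = (70/78) × 0.35 = 0.314
- variance = (70/78) × (1 + 0.35²) − 0.314² = 0.909
- effect = 0.314/√0.909 = 0.33, with power 89.2% on 78 patients

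**7. Sections side by side.** Section 12.3 treats low compliance and prohibited medication as deviations that define the per-protocol subset, leaving these patients in the FAS. Sections 9.3 and 9.4 remove the same patients from the efficacy analysis altogether. Both cannot hold. If 9.3 governs, a patient who stops well before 11 applications is removed by stated text, and no model on the diary would bring that patient back.

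**The case against.** **A Day 15 endpoint is legitimate, and the sizing matches it.** This stands. Section 12.1 plans two assessments and concludes "As a consequence 70 evaluable patients are needed for the study". Replacement holds that number, so planned power is not at risk at the expected loss. Replacement does nothing, however, about which patients are left.

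**The plan inflates the effect.** A reader might infer this, but the documents give no drop-out pattern and do not support it. Upward bias needs drop-outs to have done worse, for instance by leaving for lack of relief. Patients who leave because their pain resolved bias the result downward.

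**Ignoring the diary wastes much precision.** A reader might also infer this, and might note that averaging Days 9–15 would raise power at 70 patients to 92–97% (assumed within-week correlation 0.9 to 0.6, correlation with baseline 0.5). That holds only if the effect is flat over the week. If improvement is linear to Day 15, the average carries 11/14 of the change and power is 77–88%, below the 89.5% of the Day 15 test. For the Day 15 contrast itself the gain is small.

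**The expected loss may not be post-enrolment loss.** The synopsis says attrition and 12.1 says screening failure. Only the first supports 10% missing Day 15 ratings. This is a fair limit on the size given here.

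**The data may not all be there.** This stands in part. The diary is reviewed at Visit 2 and collected at Visit 3, and no retrieval is described for patients who leave earlier. Conversely, a patient who misses Visit 3 may still have a Day 15 diary entry; the plan does not say which source feeds the test.

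**Conclusion.** The point holds as a risk of bias from an unaddressed gap in the primary analysis. It does not show that the effect is inflated or that power is lost.

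At 10% missing the tested mean would be between 11% too large and 9% too small for drop-out effects from none to double. It could be about 17% off in either direction (0.41 or 0.29 against 0.35) if leaving strongly follows earlier ratings. If patients doing poorly leave, the error is upward, and the false-positive rate of the NPRS test can more than double. These sizes rest on assumed drop-out effects, correlations and drop-out mechanisms, and on reading the 10% as loss after enrolment. If loss is unrelated to pain, there is no bias. The conflict between 9.3/9.4 and 12.3 stands without any assumption. The plan should be changed, because a method using ratings already scheduled is available at little cost.

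**What to change.** 1. In 12.5, make the primary analysis for **both** endpoints a likelihood-based repeated-measures model on all available daily ratings, with day as a factor and a prespecified covariance (structured, or random intercept and slope). Test the Day 15 mean against 0 for the VRS and the Day 15 minus Day 1 contrast for the NPRS. The VRS must be included because 12.2 tests it first.
2. Add a sensitivity analysis that sets patients without Day 15 data to no improvement (VRS 0, NPRS change 0), because the model corrects only part of the bias when leaving depends on the unseen value.
3. Keep the two t-tests as supportive.
4. Apply the 9.3 and 9.4 exclusions to the per-protocol set only, so that they agree with 12.3.
5. State whether the diary or the investigator's record supplies the Day 15 score.
6. Use one description of the 10% in the synopsis and 12.1.

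Cost: changes of wording in 9.3, 9.4, 12.1 and 12.5 and modest programming, with no new assessments or patients. The downsides are that the primary result then depends on a model, and that patients who leave before Visit 2 may return no diary, so for them only the sensitivity analysis helps.
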